3.5. Methods of Pooling Data

Data will be pooled across sites for all analyses. Data for selected analyses (as described in Section 5) will also be pooled across Part A and B.

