1.2. Study Design

1.2.1. Synopsis of Study Design

This is a Phase 2, multicenter, prospective, randomized, double-blind study of CD101 IV or intravenous caspofungin followed by oral fluconazole step-down therapy for treatment of subjects with candidemia and/or IC. Subjects will be randomized at about 60 sites in North America (the United States [US] and Canada) and countries in Europe.

CONFIDENTIAL Page 9 of 56

In Part A, subjects will be randomized in a 1:1:1 ratio to receive CD101 IV treatment group 1, CD101 IV treatment group 2, or IV caspofungin using an interactive web response system (IWRS). Upon meeting specified criteria, oral step-down therapy is allowed in all 3 treatment groups: oral placebo in the CD101 IV groups and oral fluconazole in the IV caspofungin group. After approximately 90 subjects have been enrolled in the mITT population in Part A, enrollment into Part A of the study will close and Part B will begin. It is expected that approximately 114 subjects need to be randomized to achieve 90 subjects in the mITT population for Part A.

In Part B, subjects enrolled under Amendment 5 will be randomized in a 2:1 ratio until there are \geq 30 subjects in the CD101 IV treatment group 1 and \geq 15 subjects in the comparator group (\geq 45 additional subjects and no more than 120 subjects). Following the results of the unblinded analysis of Part A, the Part B subjects enrolled under Amendment 6 will be randomized in a 2:1 ratio to receive the CD101 IV treatment group 2 or IV Caspofungin. Total enrollment for Part B will depend on the enrollment rate for the period between the end of Part A and the start of the Phase 3 study, which is the trigger for Part B to stop enrollment. Oral step-down therapy is allowed in both treatment groups in Part B; oral placebo in the CD101 IV group and oral fluconazole in the caspofungin group. The total IV plus oral treatment duration will be \geq 14 days and up to a maximum of 21 days total for subjects with candidemia and up to a maximum of 28 days total for subjects with IC.

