1.2.2. Randomization and Blinding

After informed consent has been obtained, subjects will be screened for study eligibility before randomization. Subjects in Part A will be assigned a subject number and randomized (1:1:1) to receive CD101 IV treatment group 1, CD101 IV treatment group 2, or caspofungin on Day 1 just prior to dosing. Subjects in Part B enrolled under Amendment 5 will be assigned a subject number and randomized (2:1) to receive CD1010 IV treatment group 1 or caspofungin on Day 1 just prior to dosing. Subjects in Part B enrolled under Amendment 6 will be assigned a subject number and randomized (2:1) to receive CD1010 IV treatment group 2 or caspofungin. Randomization will be stratified based on the method used at Screening to establish the diagnosis (blood culture/rapid in vitro diagnostic [IVD] and positive Gram stain/culture from a specimen obtained from a normally sterile site). If a subject has both a positive blood culture/rapid IVD and Gram stain/culture from a specimen obtained from a normally sterile site, the subject will be randomized within the positive Gram stain/culture from a specimen obtained from a normally sterile site stratum. The study site's pharmacist (or pharmacist designee) will obtain the study drug assignment from the IWRS. A subject is considered randomized when a randomization transaction has been recorded in the IWRS and the subject is assigned a randomization number.

All subjects and study personnel, including the Sponsor, Principal Investigator (PI), and site personnel involved in study conduct will remain blinded to by subject study medication assignment for both Part A and Part B until the study is completed and the database is locked, with the exception of the Pharmacy Monitor to monitor drug preparation and drug accountability during the study and cases in which unblinding is required due to a safety or tolerability issue. Additionally, in Part A only, some personnel including the PK analyst and an unblinded statistician, will be unblinded but will not be involved in the study conduct or the final analysis. An unblinded statistician will perform the analysis on the interim and final unblinded Part A data. To maintain study blinding, study drug preparation will be performed by an unblinded site pharmacist (or qualified unblinded personnel at the study site not involved with study procedures or evaluations).

CONFIDENTIAL Page 11 of 56

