3. GENERAL STATISTICAL METHODS

3.1. Sample Size Justification

This is an exploratory study and therefore, is not powered for inferential statistical analyses. A sufficient number of subjects are randomized to the CD101 IV and IV caspofungin treatment groups in Part A to provide an initial, substantive analysis of safety, tolerability, and estimate efficacy.

It is expected that approximately 114 subjects in Part A will need to be randomized given an estimated discontinuation rate of 20%, in order to achieve 90 evaluable subjects in the mITT population. In Part A, assuming a 73% overall success rate, the sample size of 30 subjects in the mITT population in each CD101 IV treatment group and the IV Caspofungin group will yield a 95% confidence interval (CI) for this success rate of 53.8% to 87.5%.

The addition of Part B in Amendment 5 of the protocol increased the study sample size by approximately 50% to 130% (depending on the rate of enrollment over the additional months to the staged start of the Phase 3 study and the rolling close-out of Part B). In Part B, subjects will be randomized until there are at least 30 subjects in the CD101 IV treatment groups at any dose and 30 subjects in the comparator group (≥45 additional subjects and no more than 120 subjects). In Part B, total enrollment will depend on the enrollment rate for the period between the end of Part A and the start of the Phase 3 study. With the addition of Part B subjects and assuming a 73% overall success rate, a total approximate sample size of 60 subjects in the CD101 treatment group (consisting of Group 1 from Amendment 5 and Group 2 from Amendment 6) will yield a 95% CI of 60.0% to 83.7%, and a total approximate sample size of 110 subjects in the CD101 treatment group (consisting of Group 1 from Amendment 5 and Group 2 from Amendment 6) will yield a 95% CI of 63.7% to 81.0%.

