5.3. Analysis of Efficacy

All efficacy analyses will be conducted in the mITT population for Part A, Part B, and Parts A and B combined, unless otherwise specified. Subjects will be analyzed in the treatment group to which they were randomized. By subject listings of the overall response, Investigator's assessment of response and systemic signs and symptoms assessments will be provided.

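### In the Part B and combined A+B tables, each CD101 dose sits beside caspofungin subjects partly randomised when that dose was not on offer, so a difference between the Amendment 5 and Amendment 6 periods can look like a dose difference

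*SAP*

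**What the plan says.** SAP Sections 1.2.1 and 1.2.2 set up three successive randomisation periods:

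- Part A: "In Part A, subjects will be randomized in a 1:1:1 ratio" to Group 1, Group 2 or caspofungin.
- Part B under Amendment 5: "randomized (2:1) to receive CD1010 IV treatment group 1 or caspofungin".
- Part B under Amendment 6, after the unblinded Part A analysis: "randomized (2:1) to receive CD1010 IV treatment group 2 or caspofungin".

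Section 3.5 says that data for selected analyses "will also be pooled across Part A and B". Section 5.3 runs the efficacy analyses "for Part A, Part B, and Parts A and B combined, unless otherwise specified", and Section 5.4 does the same for safety. Results are given by treatment group. Section 5.3.3.2 names the combined CD101 groups as an addition to the treatment groups, so the two doses are separate columns.

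Section 3.6 plans no covariate adjustment. The SAP text nowhere splits Part B by amendment, limits caspofungin to subjects randomised alongside a given dose, or weights by period. Some displays are planned only for A+B combined: the subgroups by prior antifungal therapy, APACHE II score and catheter status (Sections 5.3.1 and 5.3.2.2, and the last two in 5.3.2.3).

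**The concern.** Caspofungin subjects randomised under Amendment 6 could not have been assigned to Group 1, and those randomised under Amendment 5 could not have been assigned to Group 2. In the Part B table, Group 1 comes wholly from Amendment 5 and Group 2 wholly from Amendment 6, while caspofungin comes from both. Reporting Part B separately therefore does not solve the problem. The combined table carries a diluted form of the same mixture.

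If sites, case mix or supportive care change between the two amendment periods, the change enters the dose columns and the caspofungin column in different proportions. A reader who compares columns would see a dose effect that randomisation did not produce. The exact interval in each column reflects sampling error only and gives no warning of it. For subgroups tabulated only for A+B combined, no concurrent Part A display is planned as a check.

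**Working it through.** **The plan's own figures.** Section 3.1 gives 95% intervals for 73% success. Clopper-Pearson limits with x = 0.73n (not rounded) reproduce them: n=30, 53.8-87.5%; n=60, 60.0-83.7%; n=110, 63.7-81.0%. These describe one arm and contain nothing about period.

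**Inputs.** Part A has "the sample size of 30 subjects in the mITT population in each CD101 IV treatment group and the IV Caspofungin group". Part B has at least 45 "additional subjects and no more than 120 subjects". The SAP does not state how Part B divides between the amendments, so the cohort sizes and period rates below are assumptions. All arms are given identical true success within each period.

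**Illustration 1.** Success 70% / 80% / 60% in Part A / Amendment 5 / Amendment 6; 30 per arm in Part A; 20:10 in each amendment.

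Combined A+B:
- Group 1 = (30×0.70 + 20×0.80)/50 = 37/50 = 74%
- Group 2 = (30×0.70 + 20×0.60)/50 = 33/50 = 66%
- Caspofungin = (30×0.70 + 10×0.80 + 10×0.60)/50 = 35/50 = 70%

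Dose minus caspofungin is +4 and -4 points; Group 1 minus Group 2 is 8 points.

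Part B alone:
- Group 1 = 80%, Group 2 = 60%
- Caspofungin = (8 + 6)/20 = 70%

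Dose minus caspofungin is +10 and -10 points; Group 1 minus Group 2 is 20 points.

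With 70/75/65%, the columns are 72/68/70% combined and 75/65/70% in Part B, so every difference is halved.

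**Illustration 2.** The SAP's 73% in Part A and Amendment 5, an assumed 83% under Amendment 6, and an assumed 45/75 split (30:15 and 50:25).

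- Combined: Group 1 = 73%; Group 2 = (21.9 + 41.5)/80 = 79.25%; caspofungin = (21.9 + 10.95 + 20.75)/70 = 76.6%. Dose minus caspofungin is about -3.6 and +2.7 points.
- Part B: caspofungin = (10.95 + 20.75)/40 = 79.25%, against 73% and 83%. Dose minus caspofungin is -6.25 and +3.75 points, and the full 10-point drift appears between the doses.
- Non-concurrent share of the caspofungin column: for Group 1, 25/70 = 36% combined and 25/40 = 62.5% in Part B; for Group 2, 15/70 = 21% and 15/40 = 37.5%.

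**Which drift matters.** Let success instead step from 73% in Part A to 83% throughout Part B. Every Part B column is 83%, so nothing false appears there. In the combined table, equal amendment cohorts also give identical columns. With the 45/75 split, Group 1 is 78.0%, Group 2 79.25% and caspofungin 55.1/70 = 78.7%, a gap of about 1.3 points between the doses.

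**What is unaffected.** Pooled CD101 to caspofungin is 2:1 in every period. In Illustration 1, pooled CD101 = (42 + 16 + 12)/100 = 70%, equal to caspofungin. Part A tables are fully concurrent.

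**Does dropping non-concurrent caspofungin suffice?** Not in the combined table. In Illustration 1, caspofungin from Part A and Amendment 5 is (21 + 8)/40 = 72.5% against 74% for Group 1; the Group 2 counterpart is (21 + 6)/40 = 67.5% against 66%. A false 1.5 points remains because allocation is 1:1 in Part A and 2:1 in Part B. With common weights of, for example, 0.6 and 0.4, both Group 1 and its caspofungin control give 0.6×70 + 0.4×80 = 74%, and the difference is zero.

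**The case against.** The strongest reply is that no comparison is planned. Sections 3.1 and 3.7 call the study exploratory and descriptive, and Section 5.3 specifies percentages and intervals for each arm, with no between-arm difference or test. That stands: nobody should infer that a hypothesis test or formal comparison is invalid. It does not dispose of the point, because dose and control columns printed together in a randomised trial invite exactly this reading.

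A reader might also infer that these tables would drive the decision to start Phase 3. The SAP does not support that. Section 1.2.1 makes the start of Phase 3 the trigger for ending Part B enrolment, and Section 3.13 holds Part B blinded until its database lock at study completion. The move to Group 2 followed the Part A analysis, which is concurrent.

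Nor does every drift cause harm, as the step between Parts A and B shows. The Part B precision statement in Section 3.1 concerns CD101 doses taken together, a contrast free of this bias.

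The assumed rates of 80% and 60% lie on opposite sides of Part A without support in the documents, and 20:10 is below the Amendment 5 target of at least 30 and 15 in Section 1.2.1. Illustration 2 meets that target and drifts in one direction only. Random error is also large: the SAP's own interval at n=60 is about 24 points wide.

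Finally, a single caspofungin column covering both amendments is read from the SAP's silence, since table shells are not shown.

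**Conclusion.** The point holds in limited form. In the Part B table, a difference in outcome between the Amendment 5 and Amendment 6 periods appears as a dose difference. In the combined table the same occurs in diluted form, and a shift from Part A to Part B adds to it if the amendment cohorts differ in size.

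In the illustrations, the false dose-versus-caspofungin gap is 2 to 4 points combined and about 4 to 10 points in Part B. The gap between doses is 4 to 8 points combined and 10 to 20 in Part B. These figures rest on assumed drifts and cohort sizes; the documents give no evidence that a drift occurred. The structural mismatch follows from the stated allocation alone, provided that both amendments enrol and Part B is tabulated as one block. This is a low-cost improvement to descriptive tables and leaves the Part A results untouched.

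**What to change.** In SAP Sections 3.5, 5.3 and 5.4:

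- Show Part B by amendment, with each CD101 dose beside the caspofungin subjects randomised under the same amendment.
- In combined tables, set each dose against caspofungin from the same periods, applying the same period weights to both arms (Part A and Amendment 5 for Group 1; Part A and Amendment 6 for Group 2). Do not simply pool concurrent caspofungin without weights.
- Take any Group 1 versus Group 2 reading from Part A only.
- Keep the crude pooled columns as supportive, with a footnote stating which periods each column covers. Pooled CD101 against all caspofungin can stay as it is.

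The cost is one SAP paragraph and extra table columns, with no new data. The real price is precision in small amendment-specific caspofungin groups: 7/10 has an exact 95% interval of about 35-93%, against about 46-88% for 14/20.

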3.6. Adjustments for Covariates

No formal statistical analyses that adjust for possible covariate effects are planned.

3.7. Multiple Comparisons/Multiplicity

Multiplicity is not of concern for this study with a descriptive interpretation.

CONFIDENTIAL Page 29 of 56

- Subjects in the mITT population excluding those who received more than 1 dose of a systemic concomitant antifungal up to Day 14 for treatment of an infection other than candidemia/IC (with the exception of subjects who received a rescue antifungal for the treatment of candidemia). Any subjects deemed a success will be excluded if receiving more than 1 dose of systemic antifungal for any indication.
- Subjects in the mITT2 population who receive no prior antifungal therapy.
- Subjects in the mITT3 population who receive no prior antifungal therapy.

Lastly, overall response and investigator's clinical response at FU will be presented for the mITT population excluding both of the following two subsets:

- Candidemia subjects deemed successes who received more than 1 dose of a systemic concomitant antifungal up through Day 21 for treatment of an infection other than candidemia/IC (with the exception of subjects who received a rescue antifungal for the treatment of candidemia) or who received more than 1 dose of a non-study antifungal after Day 21 for the treatment of an infection other than candidemia/IC.
- IC subjects deemed successes who received more than 1 dose of a systemic concomitant antifungal up through Day 28 for treatment of an infection other than candidemia/IC (with the exception of subjects who received a rescue antifungal for the treatment of candidemia) or who received more than 1 dose of a non-study antifungal after Day 28 for the treatment of an infection other than candidemia/IC.

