5.3.1. Primary Efficacy Outcome - Overall Success at Day 14 (±1 day)

The number and percentage of subjects programmatically determined to be an overall success (mycological eradication and resolution of clinical signs of candidemia and/or IC), failure, or with an indeterminate overall response at Day 14 (±1) will be summarized by treatment group for subjects in the mITT population. Exact 2-sided 95% CIs for the percentage of subjects who achieve success in each treatment group will be determined using the Clopper-Pearson method.

The overall response summary at Day 14 (± 1 day) will also be summarized separately for the following subgroup analyses defined in Section 3.8:

- Diagnosis of candidemia only and IC (with or without candidemia)
- Geographic Region
- Hepatic Insufficiency at Screening
- Renal Function Status at Screening
- Renal Disease at Screening
- Prior antifungal therapy activity
- APACHE II score
- Catheter status at Baseline

For these subgroup analyses, exact 2-sided 95% CIs for the percentage of subjects who achieve success in each treatment group within the subgroups will be determined using the Clopper-Pearson method. If the number of subjects in the subgroup overall is <10, 95% CI will not be provided for the percentage of subjects who achieve success. The subgroup analyses by prior antifungal therapy, APACHE II score, and catheter status will only be summarized for Parts A and B combined.

The reasons for failure or indeterminate overall response at Day 14 (± 1) will be summarized by treatment group for all subjects in the mITT population with an overall response of failure or indeterminate at Day 14 (± 1).

A summary will be provided for overall response at Day $14 (\pm 1)$ excluding those subjects in the mITT population who received more than 1 dose of a concomitant antifungal (with the exception of subjects who received a rescue antifungal for the treatment of candidemia) up

CONFIDENTIAL Page 38 of 56

through Day 14 (±1) in addition to study drug. This subset to be excluded is described in Section 3.8. Exact 2-sided 95% CIs for the percentage of subjects who achieve success in each treatment group will be determined using the Clopper-Pearson method.

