5.3.2. Secondary Efficacy Outcomes

5.3.2.1. Overall Response at Day 5, Day 28 (± 2) and Follow-up

The number and percentage of subjects with an overall success, failure, and indeterminate response at Day 5 and FU will be summarized by treatment group for subjects in the mITT population. The overall response summary will also be performed by diagnosis. The overall response at Day 5 and FU will be performed for subjects with candidemia only in the mITT population and at Day 5, Day 28 and FU for subjects with IC (with or without candidemia) in the mITT population. Exact 2-sided 95% CIs for the percentage of subjects who achieve success in each treatment group will be determined using the Clopper-Pearson method. If the number of subjects with IC overall is <10, 95% CI will not be provided for the percentage of subjects who achieve success.

An additional analysis of overall response at FU will be conducted excluding subjects who received more than 1 dose of a concomitant antifungal (with the exception of subjects who received a rescue antifungal for the treatment of candidemia and/or IC) up through Day 21 (for subjects with candidemia only) or Day 28 (for subjects with IC, with or without candidemia) or who receive more than 1 dose of a non-study antifungal after Day 21 or Day 28 for the treatment of an infection other than candidemia and/or IC. This subset to be excluded is described in Section 3.8. Exact 2-sided 95% CIs for the percentage of subjects who achieve success in each treatment group will be determined using the Clopper-Pearson method.

The overall response summary at Day 5 and Follow-up will also be summarized separately for the following subgroup analyses defined in Section 3.8:

- Diagnosis of candidemia only and IC (with or without candidemia)
- Geographic Region
- Hepatic Insufficiency at Screening
- Renal Function Status at Screening
- Renal Disease at Screening

Additionally, the overall response summary at Day 28 (± 2) will be summarized only for diagnosis of IC (with or without candidemia). For each subgroup analyses, exact 2-sided 95% CIs for the percentage of subjects who achieve success in each treatment group within the subgroups will be determined using the Clopper-Pearson method. If the number of subjects in the subgroup overall is <10, 95% CI will not be provided for the percentage of subjects who achieve success.

CONFIDENTIAL Page 39 of 56

5.3.2.2. Mycological Response at Day 5, Day 14 (± 1), Day 28 (± 2) and Follow-up

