The number and percentage of subjects determined by the PI to be a clinical cure, failure, or with an indeterminate clinical response at Day 14 (±1) and at the FU visit will be summarized by treatment group for subjects. The Investigator's assessment of clinical response will also be provided by diagnosis. The Investigator's assessment of clinical response at Day 14 and FU will be performed for subjects with candidemia only in the mITT population and at Day 14, Day 28, and FU for subjects with IC (with or without candidemia) in the mITT population. Exact 2-sided 95% CIs for the percentage of subjects who achieve cure in each treatment group will be determined using the Clopper-Pearson method. If the number of subjects with IC overall is <10, 95% CI will not be provided for the percentage of subjects who achieve success.

The reasons for failure or indeterminate clinical response at Day 14 (± 1) and FU visit will be summarized by treatment group for all subjects in the mITT population.

An additional analysis of clinical response at FU will be conducted excluding subjects who received more than 1 dose of a concomitant antifungal (with the exception of subjects who received a rescue antifungal for the treatment of candidemia and/or IC) up through Day 21 (for subjects with candidemia only) or Day 28 (for subjects with IC, with or without candidemia) or

CONFIDENTIAL Page 40 of 56

who receive more than 1 dose of a non-study antifungal after Day 21 or Day 28 for the treatment of an infection other than candidemia and/or IC. This subset to be excluded is described in Section 3.8. Exact 2-sided 95% CIs for the percentage of subjects who achieve success in each treatment group will be determined using the Clopper-Pearson method.

The clinical response summaries will also be stratified separately for the following subgroup analyses defined in Section 3.8:

- Diagnosis of candidemia only and IC (with or without candidemia)
- Geographic Region
- Hepatic Insufficiency at Screening
- Renal Function Status at Screening
- Renal Disease at Screening
- APACHE II score
- Catheter status at Baseline

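### SAP 3.8 removes only antifungal-exposed successes from the supportive follow-up analyses, while 5.3.2.1 and 5.3.2.3 remove exposed subjects without an outcome condition; under 3.8 the rate can only stay equal or fall

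*SAP*

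**What the plan says.** SAP 3.8 introduces one additional FU presentation, for overall response and for the investigator's clinical response, in the mITT population less two subsets. The first is "Candidemia subjects deemed successes who received more than 1 dose of a systemic concomitant antifungal up through Day 21"; the second is "IC subjects deemed successes who received more than 1 dose of a systemic concomitant antifungal up through Day 28". In both, the antifungal must have been given for an infection other than candidemia/IC, both before and after the Day 21 or Day 28 cut. Rescue for candidemia is excepted.

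The results sections describe the same analyses differently. Section 5.3.2.1: "An additional analysis of overall response at FU will be conducted excluding subjects who received more than 1 dose of a concomitant antifungal". Section 5.3.2.3: "An additional analysis of clinical response at FU will be conducted excluding subjects who received more than 1 dose of a concomitant antifungal". Neither names an outcome. Both keep rescue recipients in, in wider terms than 3.8: "with the exception of subjects who received a rescue antifungal for the treatment of candidemia and/or IC". As their sentences are built, the other-infection condition attaches only to doses after Day 21 or 28. Both then say: "This subset to be excluded is described in Section 3.8".

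At Day 14, the main rule in 3.8 depends on exposure and indication, not on outcome, but one sentence is added: "Any subjects deemed a success will be excluded if receiving more than 1 dose of systemic antifungal for any indication". Section 5.3.1 describes that analysis as "excluding those subjects in the mITT population who received more than 1 dose of a concomitant antifungal", with the rescue exception but no outcome or indication condition, and also refers to 3.8.

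Section 3.10 keeps indeterminate responses in the denominator of the success or cure rate.

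**The concern.** The SAP presents one exclusion set and defines it in two ways. A programmer working from 3.8 and one working from 5.3.2.1 or 5.3.2.3 would report different rates and confidence intervals from the same data.

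The 3.8 version also selects on the outcome being estimated. Exposed subjects leave if they succeeded and stay if they did not. A reader of the table would expect the response rate among subjects not given another antifungal. What 3.8 delivers is a rate that moves in one direction only, so a drop from the full mITT figure could be taken as evidence about the other antifungals when the rule itself produces it.

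**Working it through.** **The plan's own figure.** SAP 3.1 gives exact 95% intervals for a 73% success rate. Clopper-Pearson limits with x = 0.73n reproduce them:
- n = 30: 53.8% to 87.5%
- n = 60: 60.0% to 83.7%
- n = 110: 63.7% to 81.0%

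The SAP gives no figure for the FU exclusion analyses and no exposure rate. The counts below are therefore assumptions, with 73% borrowed as a plausible FU rate.

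**The three FU differences, side by side**

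| Element | 3.8 | 5.3.2.1 and 5.3.2.3 |
|---|---|---|
| Outcome condition | Successes only | None, apart from keeping rescue recipients |
| Rescue exception | Candidemia | Candidemia and/or IC |
| Other-infection condition | Before and after Day 21/28 | After Day 21/28 only |

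**Direction under 3.8.** Let n be the mITT subjects, x the FU successes (or cures), k the exposed successes and m the exposed non-successes who were not rescued. The 3.8 rate is (x−k)/(n−k). Its change from x/n is

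(x−k)/(n−k) − x/n = −k(n−x)/[n(n−k)].

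This is never positive. It is zero only if no success is exposed or there are no non-successes.

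**Direction with all exposed removed.** The rate is (x−k)/(n−k−m). It is never below the 3.8 rate, because the numerator is the same and the denominator is no larger. It exceeds x/n when k/(k+m) < x/n, so it can move either way. The 3.8 rate is thus a lower bound on it.

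**Numbers** (assumed n = 60, x = 44, k = 11; the same subjects count as exposed under both texts):
- Full mITT: 44/60 = 73.3% (60.3 to 83.9)
- 3.8: 33/49 = 67.3% (52.5 to 80.1), whatever m is. The change is −11×16/(60×49) = −6.0 percentage points.
- All exposed removed, m = 4: 33/45 = 73.3% (58.1 to 85.4). Exposure is 25% in both outcome groups (11/44 and 4/16), so the rate does not move.
- All exposed removed, m = 2: 33/47 = 70.2% (55.1 to 82.7)
- True worst case, exposed successes counted as non-successes: 33/60 = 55.0% (41.6 to 67.9)

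**Range over exposure.** If a fraction q is exposed regardless of outcome, the 3.8 rule gives (1−q)p/[(1−q)p + (1−p)]. For p = 73%: q = 10% gives 70.9%, 20% gives 68.4%, 30% gives 65.4%. Removing all exposed would leave 73% in each case.

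**Day 14.** Use the same counts with m = 4, and suppose 3 of the 11 exposed successes and 1 of the 4 exposed non-successes had the antifungal for a reason other than another infection.
- 3.8 as written removes 11 successes and 3 non-successes: 33/46 = 71.7%.
- The other-infection condition applied to every outcome removes 8 and 3: 36/49 = 73.5%.
- The 5.3.1 wording removes 11 and 4: 33/45 = 73.3%.

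**The case against.** The best defence is that 3.8 governs. Sections 5.3.1, 5.3.2.1 and 5.3.2.3 all point to it, so they can be read as shortened restatements. A success-only rule also has a rationale: another antifungal can help produce a success, while a failure despite extra treatment is still a failure. The stricter Day 14 sentence for successes fits such an intent, and the result is a lower bound on the rate with all exposed removed. By-subject listings of responses and antifungals would let a reader rebuild either set.

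Part of this stands. The cross-reference favours 3.8, and the lower-bound property is real. But then the 5.3 text misdescribes the tables, and nowhere does the SAP call the rule conservative. Nor is it a worst case: that would keep exposed successes in the denominator (55.0%, not 67.3%, in the example).

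A reader might infer that the success condition has no endpoint or visit at all, so that overall success could select subjects for the clinical table and the cure rate could move either way. The SAP does not support that. The sentence introducing the bullets names FU and both responses. Sections 3.2 and 5.3.2.3 and footnote 3 of Table 3-1 all use success for the clinical endpoint. The natural reading is success or cure on the response being presented at FU.

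A reader might also infer that striking the success condition alone would bring 3.8 into line with 5.3. It would not, because the indication and rescue wording would still differ. The rescue difference is nearly inert while 3.8 covers only successes, since Tables 1-3 and 1-5 bar a success or cure after added antifungal therapy for candidemia/IC. It becomes active once the condition goes: an IC subject rescued for IC who also had more than one dose for another infection would fall outside the 3.8 exception but inside that of 5.3.

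**Conclusion.** The point holds as an internal contradiction plus a badly fixed exclusion rule. On the natural reading of 3.8, the FU rate can only equal or fall below the full mITT rate, and its fall cannot be read as the result in unexposed subjects.

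In the example the gap between the two texts is 6.0 percentage points if exposure is unrelated to outcome, and 2.9 points (70.2% against 67.3%) if only 2 non-successes are exposed. The intervals overlap widely. These sizes rest on assumed counts; the difference in indication wording could add to the gap and is not included in the FU figures.

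The reach is limited. The study is descriptive, these are supportive tables, and neither the primary Day 14 result nor the full mITT FU results change. Nothing in the SAP shows that the rule would favour one arm; that would require different exposure between arms.

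**What to change.** Remove the success condition from both FU bullets in 3.8, so that exclusion depends on non-study antifungal exposure and not on outcome. State that rescue recipients stay in as failures. Use one identical wording of the indication condition and the rescue exception in 3.8, 5.3.2.1 and 5.3.2.3.

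If a conservative analysis is what is wanted, keep every mITT subject, count exposed successes or cures as non-successes on the endpoint analysed, and label the table accordingly.

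At Day 14, align the added success-only sentence in 3.8 with 5.3.1, or label it as a conservative rule and say so in 5.3.1.

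The cost is SAP text and one exclusion flag on the same data. The denominator becomes slightly smaller (45 to 47 instead of 49 in the example), or the rate lower if the worst case is chosen. Because exposure arises after baseline, the exposure-based rate can still differ from full mITT: rescued failures are retained, and subjects who die early have less time to be exposed. The table should therefore be labelled descriptive and not be read as an effect of the other antifungals.
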